- f. serum creatinine > 1.5x ULN or estimated glomerular filtration rate (eGFR) < 60 mL/min/1.73m^2; or
- g. serum amylase or lipase > 1.5x ULN.

4. Subject has a history of new or recurrent malignancy within the past 5 years, except basal cell carcinoma of the skin, squamous cell skin cancer, or in situ carcinoma that has been adequately treated with no evidence of recurrent disease for 12 months.
5. The subject is pregnant and/or breastfeeding.
6. The subject is unable or unwilling to complete the study protocol.
7. The subject fulfills diagnostic criteria for another rheumatic (overlap) disease that may confound clinical assessments in the study. Secondary sicca or Sjögren's syndrome, antiphospholipid antibody syndrome, and overlap with rheumatoid arthritis ("rhupus") are allowed.
8. The subject is receiving treatment with any of the following within the timeframes indicated before baseline, if not otherwise previously dosed longer term according to Inclusion Criterion 9:
  - a. corticosteroids: 2 weeks;
  - b. cyclosporin, tacrolimus, methotrexate, leflunomide, azathioprine, 6-mercaptopurine, cyclophosphamide, tofacitinib, or other Janus kinase (JAK) inhibitors: 4 weeks;
  - c. biologic therapies, including belimumab, abatacept, interleukin (IL)-6, and TNF- $\alpha$  (eg, infliximab, adalimumab, certolizumab pegol, or golimumab) antagonists: 8 weeks;
  - d. rituximab or other B cell depleting therapies: 6 months (subjects who have been exposed to B cell depleting therapies must have a normal peripheral B cell count at baseline, if not demonstrated before); or
  - e. other drugs or biologics, including investigational products: 8 weeks or 5 half-lives, whichever is longer.
9. The subject has urgent, severe SLE disease activity, which, in the opinion of the Investigator, warrants immediate immunosuppressive therapy and would not be appropriate for the study (eg, severely active neuropsychiatric SLE warranting immediate pulse corticosteroids and/or immunosuppressants such as cyclophosphamide, which makes the possibility of receiving placebo an inappropriate risk).

10. The subject has ongoing participation in another therapeutic clinical trial.
11. The subject has a known hypersensitivity to brentuximab vedotin, component thereof, or excipient contained in the drug formulation.

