## 6.2.2 Response Definitions

The following definitions will be used to evaluate the response assessments.

- **BILAG Clinical Response** is defined as (must meet both criteria):
  - BILAG C scores or better in all organ domains; and
  - no new BILAG A or B scores in any organ domain.
- **Systemic Lupus Erythematosus Responder Index (SRI)** definition of response includes:
  - reduction in Safety of Estrogens in Lupus Erythematosus National Assessment (SELENA)-SLEDAI of at least 4 points;
  - no new BILAG A organ domain scores and no more than 1 new BILAG B score; and
  - no worsening (increase of < 0.3) in PhGA versus baseline.
- **BILAG-based Combined Lupus Assessment (BICLA)** definition of response includes:
  - BILAG-2004 improvement (all A scores at baseline improved to B/C/D, and all B scores improved to C or D);
  - no worsening in disease activity (no new BILAG-2004 A scores and  $\leq$  1 new B score);
  - no worsening of total SLEDAI-2K score from baseline;
  - no significant deterioration (< 10% worsening) in 100 mm visual analogue PhGA; and
  - no treatment failure (defined as nonprotocol treatment [ie, new or increased immunosuppressives or antimalarials or increased or parenteral corticosteroids] or premature discontinuation from study treatment).
- **Active renal disease** is defined as either:
  - both of urinary protein:creatinine ratio  $\geq$  0.5 and active urinary sediment as defined by at least one of the following (in the absence of urinary tract infection):
    - more than 5 red blood cells (RBCs)/high power field (hpf) (or above the reference range for the laboratory),

- more than 5 white blood cells (WBCs)/hpf (or above the reference range for the laboratory), or
- presence of cellular casts (RBC or WBC); or
- isolated severe proteinuria without active sediment (eg,  $\geq 3.5$  grams/day or equivalent).
- **SELENA SLE flare** definitions include:
  - SELENA mild/moderate flare:
    - a change in SLEDAI  $\geq 3$  points,
    - new/worse skin, stomatitis, serositis, arthritis, or fever,
    - increased prednisone  $< 0.5$  mg/kg/day,
    - added NSAID/hydroxychloroquine, or
    - $\geq 1.0$  increase in PhGA (on a 0 to 3 scale);
  - SELENA severe flare:
    - change in SLEDAI  $> 12$ ,
    - new/worse CNS-SLE, vasculitis, nephritis, myositis, platelet count  $< 60,000/\mu\text{L}$ , hemolytic anemia with hemoglobin  $< 7$  mg/dL, requiring doubling or  $> 0.5$  mg/kg/day prednisone,
    - hospitalization for SLE,

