    - prednisone  $> 0.5$  mg/kg/day,
    - new immunosuppressive, or
    - increased PhGA to  $> 2.5$ .
- **BILAG SLE flare** definitions include:
  - BILAG flare:
    - development of any new BILAG A domain score, or
    - $\geq 2$  new BILAG B domain scores;
  - BILAG severe flare: development of any new BILAG A domain score.

- **Renal flare** is defined as any of these 3 events:
  - increased proteinuria, as defined by:
    - a urinary protein:creatinine ratio  $> 0.5$ , provided the 24-hour urine protein (if done) contains a total of at least 500 mg of protein, OR
    - a reproducible increase in 24-hour urine protein levels to:
      - $> 1,000$  mg if the baseline value was  $< 200$  mg,
      - $> 2,000$  mg if the baseline value was between 200 and 1,000 mg, or
      - more than twice the value at baseline if the baseline value was  $> 1,000$ ;
  - impaired renal function, as defined by a reproducible decrease in eGFR of  $> 20\%$ , accompanied by proteinuria ( $> 1,000$  mg/24 hours), hematuria ( $\geq 4$  RBCs/hpf or above the reference range for the laboratory), and/or cellular (RBC and WBC) casts; or
  - new hematuria, as defined by a new, reproducible hematuria ( $\geq 11$  to 20 RBCs/hpf) or a reproducible increase in hematuria by 2 grades compared with baseline, associated with  $> 25\%$  dysmorphic RBCs, glomerular in origin, exclusive of menses, accompanied by either an 800 mg increase in 24-hour urinary protein levels or new RBC casts.

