#### **6.2.3.3 Exploratory**

Exploratory efficacy outcomes include the following:

- proportion of subjects achieving a BICLA response at Day 85;
- proportion of subjects achieving a BILAG clinical response at Day 85
- proportion of subjects achieving a BILAG partial clinical response at Day 85, defined as BILAG C scores or better;

- proportion of subjects achieving a BILAG partial clinical response at Day 85, defined as a maximum of 1 BILAG B score or better;
- proportion of subjects achieving a SLEDAI clinical response at Day 85, defined by a  $\geq 4$  point improvement from baseline;
- proportion of subjects achieving organ-specific BILAG clinical response and partial clinical responses at Day 85 as determined by organ domain-specific scores;
- proportion of subjects achieving 20%, 50%, 70%, and n% (ACR20, ACR50, ACR70, and ACRn, respectively) improvement in SJC and TJC at Days 22, 43, 64, 85, 106, and 127;
- mean and median of observed and percentage change from baseline in SLEDAI, CLASI, TJC, SJC, PtGP, PtGA, PhGA, hsCRP, and ESR at Days 22, 43, 64, 85, 106, and 127;
- mean and median of observed and percentage change from baseline in organ domain-specific SLEDAI scores at Days 22, 43, 64, 85, 106, and 127;
- mean and median of observed and percentage change from baseline in HAQ-DI, SF-36, SF-36 Physical Component Summary (PCS), SF-36 Mental Component Summary (MCS), and FACIT-F at Days 43, 85, and 127;
- mean and median of observed and percentage change from baseline in urinary sediment (cellular casts, pyuria, hematuria), proteinuria (protein/creatinine ratio), and eGFR at Days 22, 43, 64, 85, 106, and 127; and
- mean and median of observed and percentage change from baseline in urinary sediment (cellular casts, pyuria, hematuria), proteinuria (protein/creatinine ratio), and eGFR at Days 22, 43, 64, 85, 106, and 127 in subjects with active renal disease at baseline.

Additional possible exploratory efficacy outcomes include the following:

- median time to treatment failure as defined by:
  - death or need for additional immunosuppressive therapy, or
  - death, end-stage renal disease, doubling of serum creatinine, or SLE or renal flare;
- incidence at Days 22, 43, 64, 85, 106, and 127 of SLE flares using the SELENA and BILAG definitions;
- median time to first mild/moderate and severe SLE flares using SELENA and BILAG definitions;
- incidence at Days 22, 43, 64, 85, 106, and 127 of renal flares;

- median time to first renal flare;

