### 6.3.5 Clinical Laboratory Evaluations

Samples will be drawn for both central and local laboratories. Local laboratory testing will include institutional standard tests for evaluating safety and making clinical decisions.

The following laboratory assessments will be performed by the central laboratory (unless otherwise specified) to evaluate safety at scheduled time points (see [Table 3](#)) during the course of the study:

- CBC with differential: hemoglobin, hematocrit, RBC count, mean corpuscular hemoglobin, mean corpuscular hemoglobin concentration, mean corpuscular volume, red cell distribution width, WBC count with 5-part differential (neutrophils, lymphocytes, monocytes, eosinophils, and basophils), and platelet count;

Note: The results of the CBC must be available prior to administration of each dose; therefore, testing at these time points may be done by a local laboratory to facilitate availability of the results. In addition, separate CBC samples at all specified time points should be collected for central laboratory testing.

- B cell count as quantified by CD19+ cells on flow cytometry, if applicable (for subjects with prior B cell depletion therapy, see [Table 3](#));
- HbA1c;
- chemistry panel: sodium, potassium, chloride, bicarbonate, blood urea nitrogen, creatinine, uric acid, albumin, eGFR, glucose, total bilirubin, direct bilirubin, AST, ALT, alkaline phosphatase, lactate dehydrogenase, amylase, lipase, and creatine phosphokinase;
- eight-hour fasting lipid panel: total cholesterol, triglycerides, high-density lipoprotein, and low-density lipoprotein;
- urinalysis: dipstick urinalysis, spot urinary protein and creatinine, and microscopic examination of the urinary sediment; and
- pregnancy test for WOCBP (Note: testing will be performed locally only and results will be available prior to dosing).

In addition, viral serology (HIV, hepatitis B surface antigen, anti-hepatitis B surface antibody, anti-hepatitis B core antibody, hepatitis C, and JCV) and tuberculosis (QuantiFERON-TB Gold or tuberculin purified protein derivative) tests will be performed at screening only.

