15.3.10. RENAL FLARES

Renal flares are defined as in Section 6.2.2 of the study protocol, and occurrences are captured on the eCRF.

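### Renal flare: the spot protein:creatinine limb has no baseline condition, so a subject who enters with a ratio above 0.5 can be counted as a flare while stable or improving

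*Protocol*

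**What the plan says.** Protocol 6.2.2 states that renal flare "is defined as any of these 3 events": increased proteinuria, impaired renal function, or new hematuria. Increased proteinuria has two limbs joined by OR.

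- **Spot limb.** A protein:creatinine ratio above 0.5, "provided the 24-hour urine protein (if done) contains a total of at least 500 mg of protein".
- **24-hour limb.** A reproducible rise to a level that depends on baseline: above 1,000 mg from a baseline under 200 mg; above 2,000 mg from 200 to 1,000 mg; and "more than twice the value at baseline if the baseline value was" above 1,000 mg.

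The scheduled urine test in Protocol 6.3.5 is "urinalysis: dipstick urinalysis, spot urinary protein and creatinine, and microscopic examination of the urinary sediment". No 24-hour collection is scheduled.

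The renal laboratory exclusion in Protocol 4.4.2 is "serum creatinine > 1.5x ULN or estimated glomerular filtration rate (eGFR" below 60); proteinuria is not excluded. Protocol 6.2.3.3 plans renal summaries "in subjects with active renal disease at baseline". One route to that status, in 6.2.2, is "both of urinary protein:creatinine ratio" at or above 0.5 and active sediment; the other is isolated severe proteinuria.

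SAP 15.3.10 reads: "Renal flares are defined as in Section 6.2.2 of the study protocol, and occurrences are captured on the eCRF". It then applies the SRI analysis set and Kaplan-Meier estimation to these flares.

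**The concern.** A flare is meant to be a worsening. The spot limb tests a level, and its one proviso (at least 500 mg in a 24-hour collection, if there is one) is also a level. Neither can tell a rise from a raised value that was there at entry. Since only spot urine is scheduled, this limb will usually be the one that can be evaluated.

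At stake are renal flare incidence at Days 22 to 127, time to first renal flare, and the SAP analyses built on them: Fisher tests, relative risks, logistic regression on dose, and flare-free survival. With 8 subjects planned per dose and 8 pooled placebo subjects, one or two misclassified subjects change the picture. Dose cohorts enroll one after another, so randomization within a cohort does not balance baseline proteinuria between doses.

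**Working it through.** The documents give no event rate or power figure for renal flare, so there is no stated number to reproduce. The check applies the rule as written, then sizes the effect.

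**1. Which criteria refer to change**

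- 24-hour protein: yes, tiered by baseline.
- Impaired renal function: yes, an eGFR fall of more than 20%.
- Hematuria: yes, new or up by 2 grades.
- Spot ratio: no.
- SAP 15.3.8 and 15.3.9: the SLEDAI and PhGA items of the SELENA flare and both BILAG flares are tied to baseline. SAP 15.3.10 adds nothing similar.

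**2. The rule applied to illustrative courses**

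The ratios are invented for illustration. For the 24-hour limb, a ratio of 1.0 is taken as about 1,000 mg per 24 hours (assumption). No 24-hour result under 500 mg is assumed.

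| Ratio at baseline; Days 22, 43, 64, 85, 106, 127 | Spot limb met after baseline | 24-hour limb met | Spot limb if baseline must be ≤ 0.5 |
|---|---|---|---|
| 3.0; 2.4, 1.9, 1.5, 1.1, 0.8, 0.6 | all 6 visits | never | never |
| 0.8 throughout | all 6 visits | never | never |
| 0.9; 0.8, 0.7, 0.6, 0.45, 0.4, 0.4 | Days 22, 43, 64 | never | never |
| 0.2; 0.2, 0.3, 0.7, 0.7, 0.6, 0.5 | Days 64, 85, 106 | never | Days 64, 85, 106 |
| 0.4 throughout | never | never | never |

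In the first row the 24-hour limb would need more than 2 × 3,000 = 6,000 mg, while the spot limb is met throughout a fall. A baseline condition removes the first three rows and keeps the fourth, which is a real rise.

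**3. Timing**

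SAP 15.1 counts time as event date minus randomization date. If only post-baseline visits count, the first possible event in rows 1 to 3 is at 22 − 1 = 21 days. If the Day 1 value counts, it is 0 days. The documents do not say which.

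**4. Size**

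- One subject in a group of 8: 1/8 = 12.5 percentage points. In all 32 active subjects: 1/32 = 3.1 points.
- Let f be the share entering with a ratio above 0.5. The documents give no value, so f is assumed. The chance of at least one such subject in a group of 8 is 1 − (1 − f)^8.

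| f (assumed) | Expected in 8 (8f) | At least one in 8 |
|---|---|---|
| 10% | 0.8 | 1 − 0.9^8 = 57% |
| 20% | 1.6 | 1 − 0.8^8 = 83% |
| 30% | 2.4 | 1 − 0.7^8 = 94% |

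These figures count subjects at risk of misclassification. For a given f they bound the false flares from above, because a subject may fall to 0.5 or lower, may not be recorded as a flare, or may have a genuine flare.

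**The case against.** The best defense is that flares are recorded on the eCRF and not programmed from the laboratory ratio. The criterion is titled as an increase, so an investigator may decline to record a flare when the ratio is falling. That stands as a limit: misclassification is permitted, not certain. It does not rescue the rule, because no written instruction requires a rise and about 20 sites could read it differently.

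Second, renal change is also analyzed directly. SAP 15.3.19 models the protein:creatinine ratio and eGFR as change with a baseline covariate, so a fall from 3.0 to 0.6 would show there as improvement. This limits the harm but leaves the flare tables contradicting those results.

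Third, assignment is randomized within cohorts, and no systematic direction between active and placebo is shown. That is fair; the effect may be mainly noise and dilution.

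Some stronger readings may tempt a reader, but the documents do not support them.

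- **Everyone with proteinuria is in flare from Day 1.** Only a ratio above 0.5 is affected, not one at or below it or one with a 24-hour result under 500 mg. Protocol incidence starts at Day 22, and neither document says that a Day 1 value is an event.
- **The endpoint shows only who entered with proteinuria.** For subjects entering at or below 0.5, crossing 0.5 is a rise, and the eGFR and hematuria events already require change. The endpoint is contaminated, not replaced.
- **Treatment failure is contaminated too.** Renal flare is part of one possible definition in Protocol 6.2.3.3, but the definition in SAP 15.3.13 does not contain it.

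**Conclusion.** The point holds as a defect in the written rule. The spot limb lets a subject who enters above 0.5 be counted as a renal flare at each later visit above 0.5, whether stable or improving, and the SAP carries this over without a baseline condition. Each misclassified subject is worth 12.5 points in a group of 8. The chance that a group contains at least one subject at risk is 57% to 94% for an assumed entry share of 10% to 30%, which is an upper bound on the chance of a false flare from this cause.

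The reach is limited to exploratory renal flare incidence and time to flare. Safety, the Day 85 SRI response and the SAP's treatment-failure analysis do not use the definition. Protocol 2.4 says that findings may help guide later studies, possibly in nephritis, but it names no endpoint, so it would be too much to say that the next decision rests on renal flare. The correction is worth making because it is cheap and the rule as written can label improvement as worsening.

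**What to change.** In Protocol 6.2.2 and SAP 15.3.10:

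1. Count a ratio above 0.5 as increased proteinuria only when the baseline ratio was 0.5 or lower.
2. For a baseline ratio above 0.5, require a reproducible rise from baseline. The sponsor should set the spot-ratio threshold to agree with the existing 24-hour tiers. A plain doubling rule for every such baseline would not agree: with a ratio of 1.0 taken as about 1,000 mg, a baseline of 0.6 would qualify above 2 × 0.6 = 1.2, whereas the existing tier for 200 to 1,000 mg needs about 2.0.
3. State that only post-baseline visits can give an event.
4. Check proteinuria flares recorded on the eCRF against the central-laboratory ratio at baseline and at each visit. The eGFR and hematuria events can stay as recorded on the eCRF.

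The cost is a short text change and a small amount of extra programming. Spot protein and creatinine are already scheduled at Day 1 and at Days 22, 43, 64, 85, 106 and 127, so no new data are needed. Fewer flares will be recorded.

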### **6.2.3 Efficacy Endpoints**

#### **6.2.3.1 Primary**

Not applicable to this study.

#### **6.2.3.2 Secondary**

The secondary endpoint is the proportion of subjects achieving an SRI response at Day 85.

#### **6.2.3.3 Exploratory**

Exploratory efficacy outcomes include the following:

- proportion of subjects achieving a BICLA response at Day 85;
- proportion of subjects achieving a BILAG clinical response at Day 85
- proportion of subjects achieving a BILAG partial clinical response at Day 85, defined as BILAG C scores or better;

- proportion of subjects achieving a BILAG partial clinical response at Day 85, defined as a maximum of 1 BILAG B score or better;
- proportion of subjects achieving a SLEDAI clinical response at Day 85, defined by a  $\geq 4$  point improvement from baseline;
- proportion of subjects achieving organ-specific BILAG clinical response and partial clinical responses at Day 85 as determined by organ domain-specific scores;
- proportion of subjects achieving 20%, 50%, 70%, and n% (ACR20, ACR50, ACR70, and ACRn, respectively) improvement in SJC and TJC at Days 22, 43, 64, 85, 106, and 127;
- mean and median of observed and percentage change from baseline in SLEDAI, CLASI, TJC, SJC, PtGP, PtGA, PhGA, hsCRP, and ESR at Days 22, 43, 64, 85, 106, and 127;
- mean and median of observed and percentage change from baseline in organ domain-specific SLEDAI scores at Days 22, 43, 64, 85, 106, and 127;
- mean and median of observed and percentage change from baseline in HAQ-DI, SF-36, SF-36 Physical Component Summary (PCS), SF-36 Mental Component Summary (MCS), and FACIT-F at Days 43, 85, and 127;
- mean and median of observed and percentage change from baseline in urinary sediment (cellular casts, pyuria, hematuria), proteinuria (protein/creatinine ratio), and eGFR at Days 22, 43, 64, 85, 106, and 127; and
- mean and median of observed and percentage change from baseline in urinary sediment (cellular casts, pyuria, hematuria), proteinuria (protein/creatinine ratio), and eGFR at Days 22, 43, 64, 85, 106, and 127 in subjects with active renal disease at baseline.

Additional possible exploratory efficacy outcomes include the following:

- median time to treatment failure as defined by:
  - death or need for additional immunosuppressive therapy, or
  - death, end-stage renal disease, doubling of serum creatinine, or SLE or renal flare;
- incidence at Days 22, 43, 64, 85, 106, and 127 of SLE flares using the SELENA and BILAG definitions;
- median time to first mild/moderate and severe SLE flares using SELENA and BILAG definitions;
- incidence at Days 22, 43, 64, 85, 106, and 127 of renal flares;

- median time to first renal flare;
- mean and median of observed and percentage change from Day 85 in SLEDAI, CLASI, TJC, SJC, PtGP, PtGA, PhGA, hsCRP, and ESR to Days 106 and 127;
- mean and median of observed and percentage change from Day 85 in HAQ-DI, SF-36, SF-36 PCS, SF-36 MCS, and FACIT-F to Day 127;
- mean and median of observed and percentage change from Day 85 in urinary sediment (cellular casts, pyuria, hematuria), proteinuria (protein/creatinine ratio), and eGFR to Days 106 and 127; and
- mean and median of observed and percentage change from Day 85 in urinary sediment (cellular casts, pyuria, hematuria), proteinuria (protein/creatinine ratio), and eGFR to Days 106 and 127 in subjects with active renal disease at baseline.

## **6.3 Safety Assessments**

The assessment of safety during the course of this study will consist of the surveillance and recording of AEs, including SAEs; recording of concomitant medications; physical and neurological examination findings; ECG recordings; and measurements of vital signs and protocol-specified laboratory tests. In addition, subjects will be closely monitored for signs and symptoms suggestive of neuropathy or PML.

### **6.3.1 Adverse Events**

#### **6.3.1.1 Definitions**

##### **Adverse Event**

According to the International Council for Harmonization (ICH) E2A guideline Definitions and Standards for Expedited Reporting, and 21 Code of Federal Regulations (CFR) 312.32, Investigational New Drug (IND) Safety Reporting, an AE is any untoward medical occurrence in a patient or clinical investigational subject administered a medicinal product and which does not necessarily have a causal relationship with this treatment.

The following information should be considered when determining whether or not to record a test result, medical condition, or other incident on the Adverse Events and Pre-existing Conditions CRF.

- All AEs and SAEs, including AEs of special interest (eg, new-onset neuropathy or suspected cases of PML), that occur from the time of informed consent through the follow-up visit should be recorded.

- Changes in medical conditions and AEs, including changes in severity, frequency, or character, during the safety reporting period should be recorded.
- In general, an abnormal laboratory value should not be recorded as an AE unless it is associated with clinical signs or symptoms, requires an intervention, results in an SAE, or results in study termination or interruption/discontinuation of study treatment. When recording an AE resulting from a laboratory abnormality, the resulting medical condition rather than the abnormality itself should be recorded (eg, record “anemia” rather than “low hemoglobin”).

